Ketamine is water and lipid soluble. It is absorbable by IV, intramuscular, intranasal, subcutaneous, epidural, oral, and rectal routes of administration. Differences in the effects of ketamine are entirely determined by the degree and rapidity of absorption. Ketamine's relatively low binding capacity to plasma proteins leads to rapid brain uptake and distribution (Weber et al. 2004). The differences in bioavailability are due to gastrointestinal absorption and first-pass metabolism. The α -elimination phase half-life is only 11 minutes, while the β -elimination phase is about 2.5 hours (Wieber et al., 1975).

Ketamine undergoes extensive hepatic metabolism. It is N-demethylated by cytochrome P450 enzymes in liver microsomes into NK and other metabolites (Hijazi and Boulieu 2002). The principal isoform responsible for demethylation is CYP3A4, with minor contributions by CYP2B6 and CYP2C9 (Hijazi and Boulieu 2002). NK plasma levels are about three times higher after oral administration than after IV administration. The metabolites of nor-ketamine primarily undergo renal excretion; about 91 % of ketamine is excreted in the urine as metabolites, and 1–3 % is found in the feces (Chang and Glazko 1974). Parenteral ketamine (as hydrochloride) is rapidly distributed throughout the body into widely perfused tissues, including the brain. It is likely

excreted into breast milk and does cross the placenta. However, it was posited to have no clinically relevant or adverse effects on neonates (Little et al., 1972). As this was early work and related to anesthesia, this remains an open issue for often repeated psychiatric use by pregnant or lactating mothers.

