at 2.1 hours and for the metabolite—norketamine at 1.2 hours—this from a ketamine study in children indicating the safety of this medicine (Herd et al 2002). Samples will be collected prior to injection for baseline measurement, and timed at 3, 6, and 9 hour intervals--choosing the maximum half-life duration. Two dosages will be administered: 0.5ml/kg and 1.0ml/kg. administered Intramuscularly (IM). Each administration will be separated by a minimum of 3 days and preferably one week.

The study subjects participants to greater than minimal risk because the protocol design calls for administration of IM ketamine. While the safety of IM ketamine administration is well established over decades of use, participants will be provided with full information on risks.

SEE PACKAGE INSERT FOR THIS MANUFACTURER—ATTACHED.

The IM route confers rapid onset—2-5 minutes for effect and a reliable approximate 95% absorption of ketamine. The dosage range for a 50 kg woman amounts to 25-50mg and for a 70kg woman 35mg-70mg, both quantities well within commonly used therapeutic administration of IM ketamine for depression and other psychiatric diagnoses (Dore et al, 2019).

While psychiatric use of ketamine may well exceed 1.0 mg/kg, blood concentrations of ketamine for anesthetic use have tended to follow a linear pattern of concentration, enabling estimates of concentration in breast milk, should there be a decision to exceed 1.0mg /kg IM in clinical practice.

Inclusion Criteria

Obtained by Interview/Self-Report

- • Age 21-45
- • Postpartum with established lactation for a minimum of 3 months.
- • Ability to pump breast milk and to provide a reservoir for infant feeding prior to the study; or acceptance of bottle feeding by the infant.
- • In good health—normal BP/P; afebrile-temp ascertained; review of systems by MD; absence of diagnosed illnesses.
- • Not pregnant--Pregnancy tested for before each administration by urine assay.

Exclusion Criteria:

- • Hypertension with a BP greater than 145/90
- • Subjects must be offAbsence of all psychiatric medications specifically; medications and supplements, or evaluated by the PI for non-interference
- • No alcohol or other substances such as marijuana for 72 hours or more.
- • Weight <50kg or > 90kg.
- • Pregnancy

Method of Subject Identification and Recruitment

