Two of the investigators have close connections to practicing OB/GYNs, one being one of these himself; and the other has a practice with postpartum women in part at a local university medical school. As only 4 subjects will take part, with the possibility of drop-out

requiring further recruitment this 'n' is compatible with the outreach potential of the Investigators. Lactating patients and staff in both situations will be approached for an initial screening conversation.

No advertising is involved.

Procedures

Initial screening for participation will be conducted by an investigator, via telephone.

The IC and Intake form will be emailed/mailed to a potential participant based on the suitability for admission to the study as per the screening determination. The intake form assesses current and previous illnesses, psychiatric conditions, medications, supplements and emergency contacts, etc.

Review of the Intake form will occur prior to the formal Intake Interview to be performed at the site. This review will again determine potential eligibility.

The intake Interview at the site will take place with two investigators present and will take as long as necessary to review the protocol, the IC, the information on the actual Intake form, and to determine admission to the study. This will enable Investigators to screen potential subjects prior to enrollment—as is our general practice. The Informed Consent will be provided along with the Intake Form for review by the subjects prior to making a decision to proceed with the study intake process. Subjects will discuss, and make a decision to sign, or not, the Informed Consent.

HIPAA confidentiality will be maintained throughout. Subjects will be given a numerical designation for all materials, other than the written forms discussed herein. All written and confidential materials will be stored in a locked file on premises available only to the Investigators.

Preliminary lab tests, BP and PR and an initial pregnancy test will be performed.

BP and PR will be performed at 1 hour post-administration to assess peak impact on cardiovascular status.

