This study will assess if the rapid elimination of ketamine facilitates a short and tolerable suspension of breastfeeding. If the study determines that significant amounts of ketamine remain in breast milk after 9 hours and 3 intervals, a decision will be made to add further intervals for assessment. The collection at 3 hour intervals will continue until ketamine levels are undetectable.

No hazardous substances or procedures are involved

Pumping of breast milk will be performed by the subjects, collected, and preserved as per the lab's criteria. Every attempt will be made to collect milk in volume. The study will provide a pump for collection to each participant

Subjects may stay at the clinic for the duration of the collection , or may be provided with instructions and collection materials for at home pumping if the duration is prolonged beyond 9 hours. As much as possible, tThe samples will be collected by the next day.

Subjects will refrain from eating and drinking 3-4 hours before receiving ketamine, this to prevent stomach contents that may contribute to nausea, and reduce any risk of aspiration. Subjects are permitted one cup of coffee if they are caffeine dependent, or juice or water at 3-4 hours prior. Subjects will provide consent for fasting prior to its initiation verbally and later fully in person at the clinic.

A urine pregnancy test will be conducted prior to each administration of ketamine.

A first subject in the study will have milk collected at 0, 3, 6, 9, 12 and 15 hours to determine if these intervals are sufficient to characterize a basic pharmacodynamic profile. If there is a negligible quantity in the samples as the time frame proceeds, the lab will not analyze subsequent samples. Once determined, the study will proceed with the remaining 3 subjects at the intervals projected from the first subject

Two dosages will be administered: 0.5ml/kg and 1.0ml/kg. Intramuscularly (IM). Each administration will be separated by a minimum of 3 days and preferably one week. Each session will follow the same process and procedure as described herein and occur at the study site.

PROCEDURE TIMING CHART

HOUR	PROCEDURE
-30 minutes	Arrives at Study Site Pregnancy Test Review of IC and Fasting with Consent
-!5	BP, HR, Review of Systems
0 Hour	Zero Time Pump
15	IM 0.5mg/kg; or Second Session 1.0mg/kg
15-60	Support for Subject who is reclining on sofa with eyeshades and ambient music

1 hour	BP, HR

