1-3 hours	Support for subject and integration of experience
3 hours	BP, HR, Second Pump
3-6 hours	Subject relaxing at Study Site
6 hours	Third Pump
9 hours	Fourth Pump
12 hours	Fifth Pump if necessary (as per procedure)
Home	Milk has been quantified for volume at each pump and an aliquot labelled, saved and refrigerated. If subject has gone home earlier—at 6 hours or later, subject will be contacted to pump at the assigned intervals and an aliquot refrigerated for pickup and delivery to the clinical lab for analysis.

Safety: Administration of ketamine will occur in office premises and with standard of care safety equipment available. This includes CPR trained personnel, ambu bag, defibrillator and a suction device. MDs will be present on site throughout and will administer the injections.

Injections are provided with a 25 gauge, 1 inch needle using ketamine in a sterile 100mg/ml concentration. Total volume of ketamine fluid will be less than 1 cc. Occasionally, there may be a slight bleed from the injection site. There may be mild ache at the injection site for up to a few hours. Injections are intra-muscular and into the deltoid or buttocks regions.

Subjects will be provided in advance for preliminary screening with our standard intake form to assess current and previous illnesses, psychiatric conditions, and emergency contacts, etc. This will enable Investigators to screen potential subjects prior to enrollment—as is our general practice. The Informed Consent will be provided along with the Intake Form for review by the subjects prior to making a decision to proceed with the study intake process.

At Intake, subjects will discuss, and make a decision to sign, or , the Informed Consent.

HIPAA confidentiality will be maintained throughout. Subjects will be given a numerical designation for all materials, other than the written forms discussed herein. All written and confidential materials will be stored in a locked file on premises available only to the Investigators.

No hazardous substances or procedures are involved

Methods

Quantitative analysis of ketamine will be performed by [name] PhD, Professor of Laboratory Medicine at UCSF School of Medicine and [name] at UCSF.

- 1) Lab will prepare a standard for analysis of ketamine and its principle metabolite norketamine in breast milk. The half-life of ketamine is 2.1 hours, and that of norketamine 1.2 hours (Herd et al 2007). The study will view the half-life as being a conservative 3 hours.

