1. 5) Each aliquot will be labelled with coded subject designation, concentration of ketamine administered, date, and interval. The lab will be provided with the actual quantity of ketamine administered to each subject at the 0.5 and 1.0mg/kg levels and the weight of each patient in kgs.
 - 1)
1. 6) The Lab will provide the data to KRF in formats suitable for journal publication.

INTAKE FORM ATTACHED

AS PREVIOUSLY INDICATED THERE ARE NO QUESTIONNAIRES BEING ADMINISTERED— THIS WAS DELETED FROM THE PRIOR REVISION

Inclusion Criteria

- Age 21-45
- Postpartum with established lactation for a minimum of 3 months.
- Ability to pump breast milk and to provide a reservoir for infant feeding prior to the study; or acceptance of bottle feeding by the infant.
- In good health—normal BP/P; afebrile-temp ascertained; review of systems by MD; absence of diagnosed illnesses.
- Not pregnant--Pregnancy tested for before each administration by urine assay.

Exclusion Criteria:

- Hypertension with a BP greater than 145/90
- Absence of all psychiatric medications specifically; medications and supplements, or evaluated by the PI for non-interference
- No alcohol or other substances such as marijuana for 72 hours or more.
- Weight <50kg or > 90kg.
- Pregnancy

Potential Adverse Effects

- • Nausea and vomiting—a less than 5% incidence of intolerability to ketamine.
- • Transient hypertension—BP will be monitored. In clinical practice, and in this age group, this has not occurred with any frequency.
- • Ketamine is a dissociative anesthetic and subjects have a high likelihood of experiencing dissociative effects during the first two hours following ketamine's administration. Generally, the major impact occurs in the first hour, with full recovery to baseline by 3 hours. The Investigators have conducted thousands of sessions in which dissociative effects are part of the ketamine assisted

psychotherapy (KAP) approach, including at much higher doses than those being administered in this study. Subjects may experience, an altered mental state in which there is an imaginative stream of associations, sensations and imagery. There can be anxiety accompanying a shift from ordinary reality. The Investigators have specialized in developing a transformative psychotherapy with utilization of this state and are fully equipped and experienced in dealing effectively with this state. Subjects will be prepared for the possibility of this

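### The reading meant to show peak cardiovascular impact comes 45 or 60 minutes after injection, with none scheduled in between, so it cannot be relied on to catch the peak

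*Combined protocol and SAP*

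**What the plan says.** Procedures gives one timed post-dose reading and its purpose: "BP and PR will be performed at 1 hour post-administration to assess peak impact on cardiovascular status".

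The Procedure Timing Chart gives the sequence for each session:

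- -15: blood pressure, heart rate and review of systems.
- 0 hour: zero-time pump.
- 15: "IM 0.5mg/kg; or Second Session 1.0mg/kg".
- 15-60: "Support for Subject who is reclining on sofa with eyeshades and ambient music".
- 1 hour: blood pressure and heart rate.
- 3 hours: "BP, HR, Second Pump".

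On timing of effect, Summary of Research Design gives the IM route "2-5 minutes for effect and a reliable approximate 95% absorption of ketamine". Potential Adverse Effects says of the dissociative effects: "Generally, the major impact occurs in the first hour, with full recovery to baseline by 3 hours". The same section lists transient hypertension. It undertakes to monitor blood pressure, without giving times, and reports that in clinical practice in this age group such hypertension has not been frequent. Pharmacology states for the alpha phase that the "elimination phase half-life is only 11 minutes" and for the beta phase that the "elimination phase is about 2.5 hours". No section gives a time to peak blood pressure.

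**The concern.** The sponsor's own aim for this reading is to see the peak. A peak is identified by readings on both sides of it, or by one reading known to fall on it. Here onset is within minutes, nothing is scheduled until 45 or 60 minutes later, and the time of the peak is not stated. A normal value at that point cannot separate a woman whose pressure never rose from one whose pressure rose and settled.

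What is at stake is safety information within a woman. Each participant receives 0.5 mg/kg and then 1.0 mg/kg, as little as 3 days later. A short early rise at the lower dose could go unrecorded, and the doubled dose would follow without that knowledge. Blood pressure is not an endpoint, so the measurement of ketamine in milk is not touched.

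The text and the chart also give staff two different times for the same reading.

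**Working it through.** **Step 1: the clock.** The chart's 15 carries no unit. The rows around it (-30 minutes, 15-60, then 1 hour) imply minutes. Relative to injection:

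- Pre-dose reading: -15 - 15 = -30 min.
- First post-dose reading, chart: 60 - 15 = 45 min.
- First post-dose reading, Procedures text: 60 min, a difference of 15 min.
- Next reading, chart: 180 - 15 = 165 min.

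Nothing is scheduled in the first 45 minutes (chart) or 60 minutes (text) after injection. The main point rests on this step alone.

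**Step 2: how much could be missed (illustrative).** From Pharmacology: alpha half-life 11 min, beta half-life 150 min. Assumed, because the documents do not give them:

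- the pressure rise follows plasma concentration;
- IM absorption is first-order, with half-life 5, 10, 15 or 20 min;
- the alpha phase has share f = 0.3, 0.5, 0.7 or 0.9 of the disposition curve.

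That makes 4 × 4 = 16 cases. With each rate equal to ln 2 / half-life,

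C(t) = f · ka/(ka - α) · (e^(-αt) - e^(-ka·t)) + (1 - f) · ka/(ka - β) · (e^(-βt) - e^(-ka·t)).

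Worked case, f = 0.9 and absorption half-life 5 min: ka = 0.1386, α = 0.0630, β = 0.00462 per min.

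- At 45 min: 0.9 × 1.833 × (0.0587 - 0.0020) + 0.1 × 1.034 × (0.8123 - 0.0020) = 0.094 + 0.084 = 0.177.
- At the peak, 11.1 min: 0.466 + 0.076 = 0.542.
- Ratio: 0.177 / 0.542 = 0.33.

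At the opposite corner (f = 0.3, absorption 20 min) the peak is at 55.9 min, and the reading sees 0.99 of it at 45 min and 1.00 at 60 min.

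| Over the 16 cases | Result |
|---|---|
| Time of modelled peak | 11.1–55.9 min |
| Share of peak seen at 45 min | 0.33–1.00 |
| Share of peak seen at 60 min | 0.21–1.00 |
| At least 90% of peak seen, 45 min | 6 of 16 |
| At least 90% of peak seen, 60 min | 4 of 16 |
| Best of 15 and 30 min | at least 0.895 |
| Best of 15, 30 and 60 min | at least 0.957 |

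The last two rows show why the 1-hour reading should stay: when absorption is slow, 15 and 30 min alone come too early.

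**Step 3: sensitivity to the slow half-life.** The documents also quote 2.1 h (126 min) and 3 h (180 min). With beta at 126, 150 and 180 min (48 cases) the peak is at 11.1–59.4 min, and the best of 15, 30 and 60 min still sees at least 0.957.

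**Step 4: a simpler model.** With one compartment, half-life 2.1–3 h and an assumed absorption half-life of 2–15 min, the peak falls at 12–59 min. The reading then sees 85–100% of it at 45 min and 78–100% at 60 min. The low figures in Step 2 therefore come from giving weight to the fast phase.

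**The case against.** The strongest reply is that nothing in the documents shows the peak is missed. That is right. The 2-5 minute figure is onset, the first-hour statement concerns dissociation, and concentration is only a stand-in for pressure. The 33% and 21% minima sit in one corner of an assumed grid. In that same grid the 45-minute reading sees at least 80% of peak in 10 of 16 cases, and the one-compartment model is kinder still. A reader might infer that the schedule does miss the peak, or that 6 of 16 and 4 of 16 are probabilities. Neither is supported: they are counts over values chosen to span what is unknown.

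A reader might also infer that no blood pressure precedes the 1-hour reading. The pre-dose reading shows otherwise; the gap lies only between injection and that reading. Nor should the one-third figure for transient hemodynamic changes, quoted under Pharmacology, be read as a rate for these women. It comes from pooled IV trials in depressed patients, and the investigators say transient hypertension has not been frequent in this age group.

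The safeguards are real. Normal pressure is an entry condition, physicians are on site throughout with emergency equipment, investigators stay with the woman, and the protocol undertakes to monitor blood pressure. Unscheduled readings are possible. The attached package insert is not in the text available here and may bear on monitoring.

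What stands is narrower. Presence is not measurement, a rise in pressure need not be visible in a reclining woman wearing eyeshades, and an undertaking without times does not supply a scheduled early reading.

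**Conclusion.** The concern holds in a limited form. The reading assigned to assess peak cardiovascular impact falls at 60 minutes in the text and 45 minutes on the chart, and no blood pressure or heart rate is scheduled between injection and that reading. That schedule cannot be relied on to catch a peak whose time the documents do not give. Whether it would in fact miss the peak cannot be settled from them: the modelled range runs from about a fifth or a third of peak to essentially all of it, depending on assumed absorption and alpha share and on concentration standing in for pressure. The 45-minute figure rests on reading the chart's 15 as minutes. Given healthy women, medical presence and no bearing on the milk results, this is a low-cost improvement to consider, not a flaw in the study's main aim.

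**What to change.** Add blood pressure and heart rate at 15 and 30 minutes after each injection. Keep the 1-hour and 3-hour readings. State the time of every post-dose reading from injection, identically in Procedures and in the Procedure Timing Chart. Add one sentence that the physician looks at the session 1 readings before giving 1.0 mg/kg.

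Cost: 2 readings × 4 women × 2 sessions = 16 cuff readings over 8 sessions, taken by staff already in the room, plus a few lines of text. The readings fall in the eyeshade and music period and may briefly disturb the woman; an automatic cuff would limit this. Milk collection, sample size and analysis do not change. If the sponsor declines the extra readings, the 45 and 60 minutes should still be reconciled, and the stated purpose should be softened to what that reading can show.

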Ketamine's tolerability and safety have been demonstrated over almost 5 decades. It has been used as an anesthetic for adults and children since the 1960s and has been used in neuropsychiatric research for more than two decades. Anesthetic doses from 1 to 3 mg/kg are considered to be very safe (Wan et al. 2015). Subanesthetic doses of ketamine (from 0.1 to 2 mg/kg) have been associated with transient side effects including neurocognitive, sensory-motor, and hemodynamic changes. A pooled data study from three different clinical trials of subanesthetic IV ketamine administration in MDD patients found that adverse effects common within the first four hours of administration included dizziness, derealization, and drowsiness. Whether these are truly to be considered 'adverse' or are part and parcel of ketamine's actual effects that result in the antidepressant and/or therapeutic benefits is the subject of much debate. One third of all patients experienced transient hemodynamic changes, particularly elevated blood pressure. There have been no cases of persistent neuropsychiatric sequelae, medical effects, or increased substance abuse in clinical practice. Route of administration and dose provided will also affect tolerability. While there have been multiple reports of dissociative and psychotomimetic effects of ketamine with IV and IM preparations, a trial of sublingual ketamine in 27 MDD patients reported no such side effects (Lara et al., 2013). A trial of intranasal ketamine also found only small increases in dissociative symptoms (Lapidus et al., 2014).

A cautionary here in that increasing dosages of ketamine through any route of administration will result in an increase in dissociative effects.

Ketamine has been approved by regulatory bodies worldwide for use as an anesthetic and an analgesic in both human and veterinary medicine. Ketamine was classified in 1999 as a Schedule 3 substance. Off label use has been a constant in ketamine's history.

Summary of Research Design: This study will be conducted with 4 lactating women who agree to postpone breastfeeding and provide samples of their milk. Ketamine's half-life is variously placed at 2 and a half to 3 hours. The most reliable data puts ketamine's half-life

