Subjects will refrain from eating and drinking 3-4 hours before receiving ketamine, this to

prevent stomach contents that may contribute to nausea, and reduce any risk of aspiration. Subjects are permitted one cup of coffee, juice or water at 3-4 hours prior if they are caffeine dependent. PROVIDED IN LAST VERSION

- 1) A urine pregnancy test will be conducted prior to each administration of ketamine.
- 1)
- 2) A first subject in the study will have milk collected at 0, 3, 6, 9, 12 and 15 hours to determine if these intervals are sufficient to characterize a basic pharmacodynamic profile. If there is a negligible quantity in the samples as the time frame proceeds, the lab will not analyze subsequent samples. Once determined, the study will proceed with the remaining 3 subjects at the intervals projected from the first subject. The lab will process the samples from the first subject as rapidly as possible to enable continuation of the study. Breast milk will be collected until ketamine levels are undetectable. If significant amounts of ketamine are found in samples from the 3 subsequent subjects at the last interval determined by the profile of the first subject, additional time frames for collection will be added. If necessary, the process will be repeated to fully document pharmacokinetics.

As real time testing of ketamine content in breastmilk is not possible, the first subject will be the exemplar for the timing of the resumption of breast feeding based on the data obtained, such as not detectable at 9 hours, hence breast feeding may resume. For that first subject, breast feeding may resume at 18 hours, which corresponds to 9 half-lives for ketamine, 4 half-lives being the accepted timing for the absence of a molecule. This will be confirmed by lab testing as quickly as possible for the first subject.

- 3) Pumping of breast milk will be for a full expression so as not to influence concentrations in subsequent sampling intervals. The volume of breast milk will be quantified for each expression.
- 4) Milk will be refrigerated in sterile containers and aliquots of one ounce will be brought to the lab refrigerated as soon as possible. A second aliquot of each

expression will be frozen in the event of loss or spoilage of the first aliquots, site to be determined.

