Costs to the Subject and Reimbursement for Participation

Subjects will not bear any costs and will be reimbursed for travel expenses to the Study Site. Subjects will receive a stipend of \$200 for participation--\$100 paid on enrollment and \$100 paid at conclusion of the second event.

Data Analysis

As data is accumulated by the laboratory, it will be presented as both absolute quantities and graphed. Subject data will be correlated with concentration in breast milk

according to age, body weight, dosage, volume of milk collected, length of breast feeding to the time of the study—months.

Data Storage and Confidentiality

Data will be inputted at the site into an Excel digital format with a matrix with subjects as specified above. No identifying data will be inputted and the study will be fully HIPPA compliant. Subjects will be coded as follows: 1A, 2B, 3C, 4D, and so on if more than 4 subjects are included in the Study. Access to this data will be restricted to Investigators and stored on a limited access backup disc. ADDED Written materials will be stored at the study site in a locked file cabinet, with access controlled by the Clinical Coordinator.

Potential Treatment for a Research Related Injury

Should a research related injury occur, subjects will have full support of the Investigators for treatment based in depth, frequency and duration on the nature of that injury. Subjects have full access to the investigators by phone and email and will be contacted in follow-up directly at 4 weeks after the last ketamine session.

The study will secure insurance specific to the possibilities arising to subjects as a result of their participation in the study--which will include medical coverage.

The IC includes language pertinent to arbitration should that be necessary to determine the responsibility of the study for an injury should it occur and there be a dispute.

References

Chang T, Glazko AJ (1974) Biotransformation and disposition of ketamine. *Int Anesthesiol Clin* 12(2):157–178

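### The protocol asks whether breastfeeding need be suspended only briefly, but its planned analysis of 4 women makes no allowance for variation between women

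*Combined protocol and SAP*

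**What the plan says.** The Purpose section gives the objective as measuring the presence and concentration of ketamine in breast milk, and says the information matters for treating lactating women. Procedures adds the question of duration: "This study will assess if the rapid elimination of ketamine facilitates a short and tolerable suspension of breastfeeding". It also sets the end of sampling: "The collection at 3 hour intervals will continue until ketamine levels are undetectable".

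The Summary of Research Design fixes the size: "This study will be conducted with 4 lactating women who agree to postpone breastfeeding and provide samples of their milk". The recruitment section supports that number only by saying that "this 'n' is compatible with the outreach potential of the Investigators".

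Data Analysis is brief. Of the laboratory data it says "it will be presented as both absolute quantities and graphed". It then plans to correlate milk concentration with age, body weight, dosage, milk volume and months of breastfeeding. It gives no interval, prediction or tolerance limit, no estimate of between-woman variability and no fitted half-life. It has no rule for turning four profiles into a suspension time. The protocol states no assay detection limit and does not define a negligible or a significant amount.

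Methods, item 2, uses the first subject as the guide for when participants resume feeding, with the example "such as not detectable at 9 hours, hence breast feeding may resume".

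**The concern.** How long feeding must be suspended is a question about women outside the study, and above all about those who clear the drug slowly. Amounts and graphs from four women describe those four. They do not say how far a fifth woman might differ. The correlations do not supply this either: they neither estimate a suspension time nor attach uncertainty to one.

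The protocol foresees use of the results beyond the sample. The Screening Script describes the study as preparation for ketamine-assisted psychotherapy in postpartum depression, the Summary of Research Design contemplates extrapolating milk levels to higher doses, and Methods, item 6, plans journal publication. If a time were quoted from four profiles without a limit, readers could take it as more certain than it is.

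**Working it through.** **Plan's own figure.** There is none to reproduce. The sample size of 4 rests on outreach, and no alpha, power, variability or precision target is given. The 95% level below is therefore my assumption.

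**Inputs from the protocol.** n = 4 women (Summary of Research Design); pumps on a 3-hour grid (Procedures); two sessions per woman, one at each dose. The scenario of 0 of 4 detectable at some hour is an inference from collecting until undetectable. It is not a stated criterion.

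**1. Exact bound for 0 of 4.** The one-sided 95% upper bound p solves (1 − p)^4 = 0.05.
- One-sided: p = 1 − 0.05^(1/4) = 0.527, or 53%.
- Two-sided: p = 1 − 0.025^(1/4) = 0.602, or 60%.
- At a one-sided 90% level: p = 1 − 0.10^(1/4) = 0.438, or 44%.
- Check: (1 − 0.527)^4 = 0.050.

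For scale, if 25% of women were still detectable, 0 of 4 would be seen with probability 0.75^4 = 0.32; if 20%, 0.80^4 = 0.41.

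The hour would itself be chosen from the data, as the first at which all four are clear. The bound survives this: if the hour is the longest of four continuous clearance times, the population share covered follows a Beta(4, 1) distribution. Its 5th percentile is 0.05^(1/4) = 0.473, so at most 52.7% are left uncovered at the same confidence.

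**2. Expected position of a fifth woman.** With five exchangeable continuous times, each is equally likely to be the longest. The chance that a new woman is slower than the slowest of four is 1/(4 + 1) = 20%. The 3-hour grid rounds times up, so the realised chance can be lower. The chance that the slowest of four reaches the population 95th percentile is 1 − 0.95^4 = 18.5%.

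**3. Unit of analysis.** Two sessions per woman do not make eight independent women. Treating them so would give 1 − 0.05^(1/8) = 31%, which understates the uncertainty.

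**4. Correlations.** With n = 4, a two-sided p < 0.05 needs |r| = t/√(t² + 2) with t(0.975, 2 df) = 4.303, so |r| ≥ 0.95.

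**5. Illustration of a prediction limit.** The upper one-sided 95% limit for a new woman is the geometric mean times exp(t(0.95, 3 df) × √(1 + 1/4) × s), where s = √ln(1 + CV²), t = 2.353 and √1.25 = 1.118. The 9 h geometric mean and the CVs are assumptions, not protocol figures.

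| Assumed CV | s | Multiplier | Limit from an assumed 9 h |
|---|---|---|---|
| 20% | 0.198 | 1.68 | 15.2 h |
| 30% | 0.294 | 2.16 | 19.5 h |
| 40% | 0.385 | 2.76 | 24.8 h |

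**The case against.** The strongest reply is that the study is a small descriptive one. Its stated objective is to measure presence and concentration, and no section promises a general suspension time, a percentile or a recommendation. That stands, and it limits the point to what should accompany any time that is reported.

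Four stronger readings are tempting, and the documents do not support them.
- A reader might infer that clearance in all four women is the protocol's criterion for a general suspension time. No section says so.
- A reader might take the 9-hour example in Methods, item 2, as the study's general inference. It concerns resumption by enrolled participants, from one exemplar woman.
- A reader might suppose that a mean time would be used, failing about half of women. No mean is planned. Collecting until undetectable, and adding times when significant amounts remain, tends to follow the slower woman. This completes the observed curves but does not bound a fifth.
- A reader might take 53% as the share expected to be detectable. It is an upper confidence limit; the expected share beyond the slowest of four is about 20%. Detectable is also not a measure of infant exposure.

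The bounds in steps 1 and 2 depend only on n, so the point may look like a complaint about sample size. It does not ask for more women: the size can stay at 4, provided the report shows what 4 can support. The protocol also leaves room to repeat the process or include more subjects, but that does not supply a summary method.

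The objection to curve fitting has force. With pumps at 3, 6 and 9 hours, a woman undetectable at 9 hours has at most two quantifiable post-dose values, which leaves no residual degrees of freedom and no check of log-linearity. Each sample is a full expression and so pools milk made over an interval. The laboratory may also stop analysing after a negligible result. A model-based limit can therefore be supportive only.

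**Conclusion.** The concern holds in a limited form. The protocol poses a question about the length of suspension, and its analysis attaches no allowance for between-woman variation to any answer. If all four women were undetectable at some hour, the data would be compatible with up to 53% of women still being detectable (one-sided 95%; 60% two-sided). A new woman would have about a 1-in-5 chance of being slower than all four. These figures assume that the four women behave as a random sample of those to whom the result is applied. The 1-in-5 figure also assumes continuous clearance times. The 15.2, 19.5 and 24.8 h limits only illustrate the effect of assumed inputs and are not estimates for this study.

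The documents do not show that a general suspension time will be declared from four women. The gap is that nothing in the plan would qualify such a time if it were reported. This is an inexpensive improvement in reporting, not a flaw that invalidates the study.

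**What to change.** Amend Data Analysis as follows, separately for each dose and each analyte (ketamine and norketamine).

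1. State the assay limit. Report each woman's time to below it as an interval between the last detectable and the first undetectable sample on the 3-hour grid. If later samples were not assayed after a small but measurable level, report the time as known only to exceed that hour.
2. At each hour, report the number of the 4 women detectable, with its exact one-sided 95% upper bound. Count women, not sessions. State how women who have already stopped collecting are counted.
3. Only where every woman has at least three quantifiable post-dose values, add as supportive a log-scale one-sided 95% upper prediction limit for a new woman (t on 3 df). State the log-linear assumption.
4. Present any suspension time together with these limits, and describe the result as descriptive for 4 women.

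The cost is a little more analysis and a less favourable stated conclusion. No subjects, visits or samples are added. This is a reporting change and proposes no clinical rule on when feeding resumes.
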